# 5. Plan of Investigation

# 5.1 Study schema

Figure 1: Study schema

Abbreviations: Mth – month; PPI – patient and public involvement; SSC- study steering committee; HES – hospital episode statistics; CPRD – Clinical Practice Research Datalink; TVN – tissue viability nurses/networks.

Abbreviations: CPRD – Clinical Practice Research Datalink; HES – Hospital Episode Statistics; Mth – month; SMG – Study management group; TVN – tissue viability nurses/networks; WS – workstream

#### 5.2 Study design

#### 5.2.1 Workstream 1: literature reviews, interviews and surveys

Workstream 1 focuses on gathering information from professionals and patients, updating previous systematic reviews and carrying out surveys among relevant professional groups of the management of severe pressure ulcers currently being provided across the NHS. The outcomes will be evidence from the reviews and respondents' answers to survey questions.

#### 5.2.1.1 Systematic reviews

Two topics will be reviewed:

- a) the effectiveness of reconstructive surgery for treating pressure ulcers;
- b) the impact of pressure ulceration on HRQoL

With respect to (a), the previous Cochrane systematic review on reconstructive surgery (12) will be updated. The previous review found no RCTs and we will extend eligibility to include:

- quasi-randomised controlled trials (studies using a system of quasi-randomisation for participant allocation);
- non-randomised studies with a clearly reported mechanism of group formation, clearly
  defined inclusion criteria and defined methods of ascertainment of eligible patients and
  their recruitment. These studies could use any data source which, over time, follows the
  trajectory of relevant participants receiving different methods of treatment to assess how
  alternative strategies may impact on outcomes. Relevant participants are defined as
  those with a pressure ulcer occurring within a defined period prior to study recruitment.

Single cohorts [Altman reference], where all participants are given the same type of surgery, and cross-sectional and case-control studies will be excluded. Despite widening eligibility, there is still a high risk of the review being "empty."

Full details are available in the review protocol. In brief, the key elements of the review questions are:

Population: Adults with a diagnosis of a pressure ulcer (stage II, III, IV or unstageable) managed in any care setting. We will exclude studies with mixed wound populations; that is studies that do not restrict inclusion to pressure ulcers only.

Intervention: Reconstructive surgery for pressure ulceration. Likely comparisons are surgery compared to no surgery and different types of surgery compared with each other. Surgical wound debridement will be considered as a co-intervention, i.e. we will not consider surgical debridement alone as a type of reconstructive surgery.

Eligible studies: RCTs and non-RCTs, as described above.

Outcomes: Primary outcomes are complete wound healing (as either a time to event or proportion of wounds completely healed), wound dehiscence and wound recurrence. Secondary outcomes are HRQoL, wound infection, cost-effectiveness and incidence of a new ulcer (separate to wound recurrence as this refers to an ulcer in a different area to the index ulcer).

Standard Cochrane Wounds search methods will be applied: risk of bias assessment using the RoB 2.0 or ROBINS-I tools; assessment of heterogeneity; synthesis of relative treatment effects including meta-analyses where justified and feasible; presentation of summary of findings tables and GRADE assessment of included evidence for pre-specified outcomes. Subgroup analysis for ulcer stage and type of surgery will be explored.

With respect to (b), we aim to assess quantitatively the effect of a pressure ulcer (stage 2 or more severe) on HRQoL, taking care to distinguish as far as possible between the effect of the pressure ulcer and the effects of other comorbidities. Making this distinction requires evidence about changes in HRQoL over time, i.e. longitudinal cohort studies (including RCTs). These studies are most likely to provide relevant information, by measuring HRQoL on multiple occasions, ideally with pressure ulcer status changing between measurements in a proportion of the people included in the study. Studies can measure healing (starting with a population of

people all of whom had a pressure ulcer, with the ulcer healing in a proportion of participants during follow-up) or prevention (starting with a population of people without a pressure ulcer but at risk of developing one, with an ulcer developing in a proportion during follow-up). Hence, RCTs of either ulcer prevention or treatment could be eligible. Eligible studies must also measure HRQoL using one or more validated HRQoL instruments.

Full details are available in the review protocol. In brief, the key elements of the review questions are:

Population: Adults with a diagnosis of a pressure ulcer (stage II, III, IV or unstageable) or at risk of developing a pressure ulcer managed in any care setting. We will exclude studies with mixed wound populations; that is studies that do not restrict inclusion to pressure ulcers only. Eligible studies: Longitudinal cohort studies, including RCTs, which measure HRQoL using a validated instrument on two or more occasions.

Exposure: Change in pressure ulcer status between HRQoL measurements. Outcomes: Validated generic HRQoL instruments are: SF-36; SF-12; SF-6; EQ-5D; Nottingham Health Profile; Sickness Impact Profile and the World Health Organization Quality of Life Scale. Studies using a validated disease-specific instrument are also eligible; the only such instrument that we are aware of is the PurPOSE PUQOL tool. Standard Cochrane Wounds search, study selection and data extraction methods will be applied.

[figure not shown]
# 5.2.1.2 Surveys among relevant professional groups of the management of severe pressure ulcers currently being provided across the NHS

We will design on-line surveys using SurveyMonkey. We will survey surgeons, nurses and general practitioners separately, i.e. surveys with varying items relevant to their roles in the care pathway. The survey for nurses will be relevant to nurses working in different settings or across settings (community or hospital), and with varying degrees of specialism with respect to the management of pressure ulcers (e.g. community nurses, TVNs, specialist secondary care nurses), applying filter questions to ensure items presented focus on issues that are most pertinent to the respondent's role.

Surgeons will be contacted through their professional bodies, e.g. British Association of Plastic, Reconstructive and Aesthetic Surgeons (BAPRAS) and the British Orthopaedic Association (BOA). Distribution lists for nursing groups may be more difficult to identify but we expect to have support from the Tissue Viability Society (which covers community and acute sectors) and the TVN2gether group, which has a wide membership. To engage community nurses, we will approach the Queen's Nursing Institute (QNI) and Royal College of Nursing District Nurses (RCN DN) Forum (https://www.rcn.org.uk/get-involved/forums/district-nursing-forum DN Forum). We will also use social media to distribute links to the survey. We aim to distribute the survey for surgeons to plastic surgeons and orthopaedic surgeons because these are the specialties under which most surgical reconstructions were coded in the anonymised HES datasets.

The key topics on which data will be collected are summarised in Figure 2. We will collect data from community-based nurses on the care they provide to patients with severe pressure ulcers, their ability to refer these patients to secondary care and to a surgeon specifically and how they make referral decisions. We will ask surgeons about the operations they perform, barriers and facilitators that drive individual decisions to operate and institutional capacity for surgery in this patient population, and personal views on reconstructive surgery for pressure ulcers.

Figure 2: Topics for items for Workstream 1 surveys about the types of people with severe pressure ulcers treated by nurses and surgeons, and how referral and treatment decisions are made

## 5.2.2 Workstream 2: efficient cohort studies of the management of severe pressure ulcers

Workstream 2 comprises quantitative analyses of two retrospective cohorts assembled from routinely collected data: (i) a HES cohort (HES data from secondary care linked with mortality data) and (ii) a CPRD cohort (CPRD Gold (primary care data) linked with HES including mortality). Both cohorts are needed because CPRD covers only 7% of the English population; the CPRD cohort alone would capture <50 patients having reconstructive surgery.

#### 5.2.2.1 HES cohort design and target population

We will request data for index admissions with a severe pressure ulcer (ICD-10 codes L89.2, L89.3, L89.9) or any pressure ulcer (L89.X) during a period of 8 years (01/04/2011-31/03/2019), linked with other HES APC and outpatient episodes and mortality data (to 31/03/2019). The target population for the HES cohort is: patients >=18 years of age in England admitted to hospital, with an ICD-10 diagnosis code for a severe pressure ulcer.

## 5.2.2.2 CPRD cohort design and target population

The request for CPRD-Gold data linked to HES and mortality data is limited to 10,000 individuals (with unlimited records per individual). Preliminary interrogation of CPRD-Gold indicated that there are ≈1,100 incident pressure ulcers (i.e. with no pressure ulcer recorded in the previous 12 months) per year recorded in CPRD, eligible for linkage to HES and mortality data. Therefore, we expect to request data for patients with an index record with a Read code

indicating an incident pressure ulcer (Table 1) during a period of eight (01/04/2011-31/03/2019) or nine years (01/04/2010-31/03/2019), subject to the limit of 10,000 individuals. All CPRD records, HES APC and outpatient episodes, and mortality data will be linked in this cohort (to 31/03/2019). The target population for the CPRD cohort is: patients >=18 years of age in England registered with a general practice with up-to-standard (UTS) registration and contributing data to CPRD, with a Read code indicating an incident pressure ulcer. No exclusions will be applied.

Table 1: Read codes to identify patients with an incident pressure ulcer

Medical code	Read code	Description
3928	M271.00	Non-pressure ulcer lower limb
4929	M270.13	Pressure sore
6862	M270.00	Decubitus (pressure) ulcer
11786	Z174P00	Pressure sore care
14995	M270.11	Bed sore
15505	39C0.00	Pressure sore
17592	39C00	Pressure sore index value
17790	Z1B3.00	Dressing of pressure sore
28380	Z9K5.00	Pressure sore prevention
28814	ZRqY.00	UK consensus classification of pressure sores 1994
35329	ZQ39.12	Pressure ulcer assessment
36995	39C4.00	Waterlow pressure sore risk score
38996	ZQ39.00	Pressure sore assessment
44641	39C1.00	Superficial pressure sore
46050	ZQ52.00	Pressure sore risk assessment
49654	ZQ39.13	Bed sore assessment
55220	ZQ39.11	Decubitus ulcer assessment
55382	39C2.00	Deep pressure sore
56610	ZRrL.00	Waterlow pressure sore risk score
63243	39C3.00	Pressure sore -deep + superfic
95113	39C6.00	Maelor pressure ulcer risk assessment score
95886	39C5.00	Medley pressure sore risk score
100638	39CA.00	EPUAP (European pressure ulcer advisory panel) grade 4 ulcer
100778	39C7.00	EPUAP (European pressure ulcer advisory panel) grade 1 ulcer
100864	39C9.00	EPUAP (European pressure ulcer advisory panel) grade 3 ulcer
101006	39C8.00	EPUAP (European pressure ulcer advisory panel) grade 2 ulcer
101713	M270200	Community hospital acquired pressure ulcer
102230	M270100	Nursing home acquired pressure ulcer
102923	M270300	Hospice acquired pressure ulcer
103207	M270000	Hospital acquired pressure ulcer
103311	38Dr.00	EPUAP (Euro pressure ulc advisry panl) classification system
104552	M270z00	Decubitus ulcer and pressure area NOS
104850	M270400	Stage I decubitus ulcer and pressure area
105150	M270500	Stage II decubitus ulcer
106686	M270600	Stage III decubitus ulcer
106902	M270700	Stage IV decubitus ulcer
108537	M270.14	Decubitus ulcer and pressure area

#### 5.2.2.3 Study setting

Pressure ulcer management in primary (CPRD cohort) and secondary NHS care (CPRD and HES cohorts).

# 5.2.2.4 Health technologies being assessed

Each cohort will allow the assessment of a variety of health technologies.

The HES cohort will assess reconstructive surgery operations coded with a variety of Office of Population Censuses and Surveys (OPCS)-4 codes. These codes are; distant flap of skin and muscle (S17), distant flap of skin and fascia (S18), distant pedicle flap of skin (S19), other distant flap of skin (S20), hair bearing flap of skin (S21), sensory flap of skin (S22), flap operations to relax contracture of skin (S23), local flap of skin and muscle (S24), local flap of skin and fascia (S25), local subcutaneous pedicle flap of skin (S26) and other local flap of skin (S27).

Surgical debridement (OPCS code S57.1) will also be described but is not the focus of the study. Usual care interventions are not coded in HES data, with some exceptions e.g. negative pressure therapy (OPCS code S57.7 Dressing of skin using vacuum assisted closure device NEC). Such interventions will also be described.

The CPRD cohort will assess usual care, including but not limited to: referrals to secondary care (identified from linked HES episode); referrals and discharges from specified forms of care within primary care (Table 2), dressing of ulcer/wound (Table 3) and negative wound pressure therapy.

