# 2.2 Surgical reconstruction of severe pressure ulcers

Surgical reconstruction is an expensive intervention; it is potentially cost-effective providing that patients recover uneventfully and do not experience a recurrence. When studying specific patient groups who may be appropriate to undergo surgical interventions for severe pressure ulcers, as per the CB, knowledge of perceived indications for, and barriers to, surgical reconstruction are critical. Full skin thickness pressure ulcers are widely considered to represent a failure of skin care to prevent them and, therefore, understanding the circumstances in which such ulcers arise is an important aspect of the evaluation of the suitability of a patient for surgical reconstruction.

Studying surgical management of severe pressure ulcers in the UK context is challenging because surgical reconstruction is very rarely carried out. Preliminary analyses using the HES data extract obtained from the University of Bristol showed that, over two years, 81,383 patients were recorded as having had an index hospital admission in England which included an ICD-10 coded diagnosis of a severe pressure ulcer. Of these, only 165 patients also had an ICD-10 code for a reconstructive surgery during the admission.

The CB specifies that one element of the research should be an "efficient cohort study to identify priorities for future research." To do this, the study team aim to characterise the current care pathway across community and secondary care. We propose two retrospective cohort studies assembled from routine sources (HES and Clinical Practice Research Datalink (CPRD) Gold) as the most efficient cohort design. Assembling the retrospective HES cohort from routine data for England will also allow us to present data for all patients who have had their pressure ulcers managed surgically over a defined time frame, as well as understanding current practices in relevant settings.

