## 2.3 Uncertainties and gaps in current knowledge

There is a dearth of evidence around the evaluation of surgical interventions for stage III and IV pressure ulcers. A Cochrane review on reconstructive surgery for pressure ulcers (12) concluded that: "Currently there is no randomised evidence that supports or refutes the role of reconstructive surgery in pressure ulcer management." NICE guidance on pressure ulcers makes no recommendations about surgical management. (1) Other guidelines recommend obtaining "a surgical consultation for possible operative repair in individuals with stage III or IV pressure ulcers that are not closing with conservative treatment". (3) This recommendation does not specify specific operations or indicate the patients likely to benefit and is based on indirect evidence or expert opinion.

There is no published data from the UK describing the number of people having reconstructive surgery, and published international cohort studies look at numbers of people in a single facility (5, 13-15)

Exploration of HES Admitted Patient Care (APC) data showed that patients who had reconstructive surgery were about 20 years younger and had fewer comorbidities than those who did not. Diagnoses in addition to the pressure ulcer showed that about half had paraplegia, tetraplegia, spinal injuries or sequelae of a transport accident. These differences were also apparent between patients who had reconstructive surgery and those who had debridement only. Reconstructive surgery was carried out in 55 of 267 hospitals (20.5%) admitting index patients; in 24 months, only two performed >10 procedures and 26 did only 1. This work also found that, prior to 2012, a single ICD-10 code L89.X was used to denote any pressure ulcer.

Exploration of CPRD showed that referrals to "district nurse service" were most common (3,045 instances in 913 patients with an incident pressure ulcer). Referrals to podiatrists were second most common (682 instances in 367 patients). Referrals to TVNs were less common (286 instances in 133 patients); this was expected since such referrals are for treatment advice rather than treatment *per se*, i.e. for patients with challenging wounds.

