## 4. Aims and objectives

The aim of the SIPS study is to clarify the Population, Intervention, Comparator and Outcome (PICO) elements needed to be defined a future RCT of reconstructive surgery for severe pressure ulcers. We define reconstructive surgery as any surgical procedure that leads to epithelial closure of the wound, typically distant or local flaps of skin and muscle/fascia.

We have designed a study with three workstreams to address uncertainties in the "PIC" elements of a future potential PICO research question about the effectiveness and cost-effectiveness of reconstructive surgery.

Workstream 1 will include literature reviews and a survey of surgeons and nurses who manage patients with severe pressure ulcers in either secondary care or community settings.

The objectives of Workstream 1 are to:

- 1. Systematically review evidence about: (a) the effectiveness of reconstructive surgery for treating pressure ulcers; (b) the impact of pressure ulceration on HRQoL.
- 2. Carry out comprehensive on-line surveys with relevant healthcare professions to:
  - Describe the characteristics of patients in the UK currently being referred for a surgical opinion about surgical reconstruction;
  - o Describe variation in the operations and postoperative care currently being provided;
  - Describe variation in usual care provided before initiation of a surgical referral.

Workstream 2 comprises retrospective cohort studies assembled from routinely collected data sources (HES and CPRD Gold). The CPRD cohort will include data about the care pathway for patients with incident pressure ulcers, from diagnosis and management in primary care to (for a minority) secondary care and, potentially, reconstructive surgery (consultations, diagnoses, interventions and referrals both within primary care, e.g. to nursing teams, and to secondary care). The HES cohort will include information on 'index' inpatient admissions assigned an ICD-10 code for a severe pressure ulcer, and subsequent HES activity (inpatient admissions and outpatient clinic attendances).

The objectives of Workstream 2 are to:

- 3. Describe in the CPRD cohort patients with incident severe pressure ulcers and their entire care pathways, e.g. usual management in the community, management by TVNs, admission to hospital and subsequent care.

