- Describe in the HES cohort patients with a diagnosis of severe pressure ulcer at the time of hospital admission, their care pathways after admission and frequencies of health outcomes.
- 5. Compare in the HES cohort outcomes in matched groups of patients who were similar on admission and who did/did not have a surgical reconstruction operation.
- 6. Explore in the matched groups subgroup interactions with reconstructive surgery that may influence outcomes, e.g. comorbidities, previous hospital admission without surgery.

[figure not shown]
Workstream 3 is a formal consensus process, separately among health professionals and patients and carers, to make recommendations about which treatments are appropriate for whom and when. The objective of Workstream 3 is to:

7. Seek consensus about which treatments and management strategies are appropriate for whom and when, given findings from workstreams 1 and 2.

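### Reconstructive surgery is defined as any procedure that closes the wound but is identified in HES only by flap codes S17 to S27, so other closures are counted as not reconstructed

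*Protocol*

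**What the plan says.** Protocol section 4 gives the concept: "We define reconstructive surgery as any surgical procedure that leads to epithelial closure of the wound, typically distant or local flaps of skin and muscle/fascia". Flaps illustrate the definition; they do not limit it.

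Protocol section 5.2.2.4 gives the rule for HES: "These codes are; distant flap of skin and muscle (S17), distant flap of skin and fascia (S18", continuing through S27. All eleven labels are flap procedures. One of them is "flap operations to relax contracture of skin (S23"). The only other procedures named there are debridement (S57.1) and, as an example of a coded usual-care intervention, vacuum-assisted dressing (S57.7). Both are to be described only.

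Objective 5 in section 4 sets the contrast: "Compare in the HES cohort outcomes in matched groups of patients who were similar on admission and who did/did not have a surgical reconstruction operation". Section 5.2.2.7 repeats it as patients who did and did not have reconstructive surgery. Neither place says how a patient whose ulcer was closed by a technique outside the list is handled.

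**The concern.** The definition and the code list do not describe the same intervention. Closure by skin graft or direct suture, for example, would satisfy section 4, yet no listed code would capture it. Because the contrast has only two sides, such a patient falls by default into the group that did not have reconstruction.

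Two outputs are affected. The first is descriptive: how often reconstruction is done, by what type, and how often it is repeated (sections 5.2.2.5 and 5.2.2.6). Section 2.2 says that the HES cohort will present all patients whose ulcers were managed surgically, and a flap-only list does not deliver that if other closures occur. The second is the comparison in objectives 5 and 6, where some comparators would have had the intervention as defined.

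S23 raises the reverse question. Its label names a different indication, so an S23 operation counted as exposure may not be ulcer closure. The study exists to settle the population, intervention and comparator of a future trial, so the boundary of the intervention is central to it.

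**Working it through.** **Inputs**
- Expected HES cohort: about 120,000 index admissions, about 220 with surgical reconstruction (section 5.2.2.6). Comparator: 120,000 − 220 = 119,780.
- Preliminary count: 165 of 81,383 index patients over two years (section 2.2: "only 165 patients also had an ICD-10 code for a reconstructive surgery during the admission").
- Number of non-flap closures, number of S23 operations, matching ratio, event rates: not given.

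**1. The plan's own figure.** 165 / 81,383 = 0.203%, and 0.203% × 120,000 = 243, against a stated figure of about 220 (220 / 120,000 = 0.183%). The two are of the same order. Both projections are rounded and the period behind the 120,000 is not stated, so the gap is not treated as an error. Nothing below depends on it.

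**2. Side by side.**

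| Patient in an ulcer-coded admission | Section 4 definition | Section 5.2.2.4 codes |
|---|---|---|
| Ulcer closed by a flap in S17 to S27 | reconstructed | reconstructed |
| Ulcer closed by another technique | reconstructed | not reconstructed |
| Contracture relaxed by a flap (S23) | not on its label | reconstructed |
| No closure | not reconstructed | not reconstructed |

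The second and third rows are the conflict.

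**3. Unmatched comparator.** Let M be the number of missed closures (assumed 22 to 220). Contamination = M / 119,780, which is 22 / 119,780 = 0.02% to 220 / 119,780 = 0.18%. This is negligible.

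**4. Matched comparator.** Assume a 1:1 set of 220, and let s be the share of missed closures drawn as matches. Contamination = M × s / 220.
- s = 5% to 10%: from 22 × 0.05 / 220 = 0.5% to 220 × 0.10 / 220 = 10%.
- s = 25% to 50%: from 22 × 0.25 / 220 = 2.5% to 220 × 0.50 / 220 = 50%.

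The width of the range shows that the documents do not settle the size.

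**5. What contamination could do.** Let c be the share of comparators with an uncoded closure and f the share of the exposed whose flap was not for the ulcer. Suppose the former carry the risk of reconstructed patients and the latter the risk of unreconstructed patients. The retained risk difference is then 1 − f − c. With assumed risks of 50% and 35%, 220 per group, and f = c = 10%:
- comparator 0.50 − 0.10 × 0.15 = 0.485
- exposed 0.35 + 0.10 × 0.15 = 0.365
- difference 0.12 instead of 0.15, that is 80% retained
- power at two-sided 5% falls from 89% to 72%

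If misclassified patients carry some other risk, the bias can go either way.

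**The case against.** The strongest reply is that flaps are described as typical, so most reconstructions are probably captured, and that the comparison may never be run. Section 5.2.2.7 makes it conditional on standardised differences below 0.2, while section 2.3 reports an age gap of about 20 years. Step g also leaves the propensity method open, so a matched set is not certain. Reporting reconstruction type by OPCS code would make any S23 contribution visible. All of this stands and limits the weight of the point. It does not remove the conflict: the code list is fixed in the protocol itself, and the frequency of surgery is affected whether or not the comparison goes ahead.

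Four stronger readings are tempting and are not supported.

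- *Flaps have no link to the ulcer.* The index admission must carry a severe ulcer code, so a link exists at admission level. Rules on site, episode or diagnosis position could properly sit in the statistical analysis plan, which is not at hand.
- *Low-volume hospitals show incidental coding.* Among the 55 operating hospitals, "only two performed >10 procedures and 26 did only 1", but rare surgery looks the same. About half of the operated patients had paraplegia, tetraplegia, spinal injury or sequelae of a transport accident, which fits genuine ulcer reconstruction. Dividing the 26 by the 165 would also mix procedures with patients and says nothing about unrelated flaps.
- *A large part of the matched comparators is contaminated.* That needs an assumed share of non-flap closures, a 1:1 ratio that the protocol does not state, and every missed closure being drawn as a match.
- *The bias is certainly towards no difference.* That holds only under assumptions like those in step 5 of the working. A flap for tumour or trauma may carry a quite different risk of death or readmission.

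**Conclusion.** The point holds as a conflict between a stated definition and a stated rule. Section 4 covers any closure and section 5.2.2.4 covers flaps only, so other closures are counted as not reconstructed, and S23 is included although its label is another indication. The frequency of reconstruction is understated, relative to the protocol's own definition, by whatever number of other closures occurs. For the comparison, neither size nor direction can be derived from the documents. Contamination is negligible in the unmatched comparator (at most 0.18% for up to 220 missed closures) and possibly material in a matched set against about 220 exposed patients. The matched figures rest on assumed values of M and s and an assumed 1:1 ratio; the power illustration also rests on assumed risks. The change is worth making because the exposed group is small and the correction is cheap.

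**What to change.** Reconcile section 4 with section 5.2.2.4 in one of two ways:

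1. Add the OPCS-4 codes for other closures, such as skin graft or direct closure, as exposure types reported separately from flaps; or
2. Restrict the definition in section 4 to flap reconstruction, and adjust the statement in section 2.2 about presenting all surgically managed patients.

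In either case, exclude patients with other closure codes from the comparator, over the same window in which exposure is counted, and report their number. Justify S23 or drop it.

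As a sensitivity analysis only, repeat the comparison restricted to flaps with a compatible site code, or with an ulcer diagnosis in the same or an earlier episode. This should not be the main rule: where coding is incomplete it could discard true reconstructions from a group of about 220. It also needs site and episode fields in the extract, which the protocol does not list and which should be confirmed.

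The cost is a small amount of coding work and the loss of a few comparators from about 120,000.

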#### 5.2.2.6 Sample size considerations

Based on the anonymised HES extracts, HES cohort A should comprise about 120,000 index hospital admissions, including about 220 in which surgical reconstruction operations were carried out and about 3,900 in which surgical debridement without reconstruction was carried out. There are also likely to be about 170 subsequent admissions in which operations were carried out over 2 years of follow-up. Usual care for patients not having surgery will be characterised precisely.

We expect the CPRD cohort to comprise about 10,000 incident pressure ulcers. Severe pressure ulcers in the community are mainly managed conservatively; few are admitted to hospital and CPRD only covers 7% of the English population. These data will be summarised descriptively, Outcome frequencies (healing, infection, referrals to community nursing teams, TVNs and secondary care) will be estimated precisely, given this sample size. We expect to be able to follow very few incident ulcers through to surgical reconstruction.

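### In the CPRD cohort, referral to secondary care is measured by a linked HES episode, which records a hospital contact and not a referral

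*Protocol*

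**What the plan says.** Section 5.2.2.4 lists, among the usual-care items for the CPRD cohort, "referrals to secondary care (identified from linked HES episode"). It states no condition on admission route, referral source, diagnosis or timing. Section 5.2.2.2 shows what those episodes are: "All CPRD records, HES APC and outpatient episodes, and mortality data will be linked in this cohort". They are therefore inpatient and outpatient contacts.

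Four other places bear on the item:

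- Section 4 says the cohort will hold data on "interventions and referrals both within primary care, e.g. to nursing teams, and to secondary care".
- Section 5.2.2.4 and Table 2 take referrals within primary care from Read codes in the GP record. No corresponding code list is given for referrals to secondary care.
- Section 5.2.2.5 lists hospital admission with an ulcer diagnosis as a CPRD outcome. It does not list referral to secondary care.
- Section 5.2.2.6 nevertheless counts it among the outcome frequencies: "Outcome frequencies (healing, infection, referrals to community nursing teams, TVNs and secondary care) will be estimated precisely, given this sample size".

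**The concern.** A referral is a decision by a clinician; a HES episode is one possible consequence of it. Using the consequence to stand for the decision creates two errors.

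- **Missed referrals.** A referral that was declined, not taken up, or overtaken by death leaves no episode, and the patient is recorded as not referred.
- **False referrals.** An emergency admission without referral leaves an episode. So does the stay in which an ulcer developed, and Table 1 includes hospital-acquired ulcers among the index codes. As written, either can count as a referral.

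This matters for Objective 3, which is to describe the whole pathway from community to hospital. Patients who were referred but never seen mark a point where that pathway stops, and the rule cannot show them. Cohort findings also feed the Workstream 3 statements on usual care, which include how long it should last before a surgical opinion is sought. A reader who relies on the precision statement could take the resulting frequency as a sound measure of referral practice.

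**Working it through.** **1. Reproduce the cohort size.** Section 5.2.2.2 gives about "1,100 incident pressure ulcers (i.e. with no pressure ulcer recorded in the previous 12 months) per year recorded in CPRD", collected "during a period of eight (01/04/2011-31/03/2019) or nine years (01/04/2010-31/03/2019), subject to the limit of 10,000 individuals". Then 1,100 × 9 = 9,900, which agrees with "We expect the CPRD cohort to comprise about 10,000 incident pressure ulcers" in Section 5.2.2.6; 1,100 × 8 = 8,800 does not. The difference has little effect on what follows.

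**2. Check the precision statement.** The 95% half-width for a proportion p is 1.96 × √(p(1 − p)/n). At n = 10,000:

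| p | half-width (points) |
|---|---|
| 2% | 0.27 |
| 5% | 0.43 |
| 10% | 0.59 |
| 20% | 0.78 |
| 50% (worst case) | 0.98 |

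At n = 8,800 the worst case is 1.04. As a statement about sampling error, precise estimation is correct.

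**3. Effect of the proxy.** Let p be the true proportion referred, Se the share of referred patients with an inpatient or outpatient episode, and F the share of unreferred patients with an episode that is counted. Counting patients, not episodes:

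- reported proportion = Se × p + F × (1 − p)
- referred patients missed = n × p × (1 − Se)
- unreferred patients counted = n × (1 − p) × F

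The documents give none of p, Se or F. The assumed ranges are p 2–20%, Se 50–100% and F 0–10%. At n = 10,000, with the half-width taken at the reported proportion:

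| p | Se | F | reported | bias (points) | half-width | missed | wrongly counted |
|---|---|---|---|---|---|---|---|
| 20% | 50% | 0% | 10.0% | −10.0 | 0.59 | 1,000 | 0 |
| 10% | 70% | 0% | 7.0% | −3.0 | 0.50 | 300 | 0 |
| 2% | 50% | 1% | 1.98% | −0.02 | 0.27 | 100 | 98 |
| 5% | 70% | 2% | 5.4% | +0.4 | 0.44 | 150 | 190 |
| 10% | 100% | 5% | 14.5% | +4.5 | 0.69 | 0 | 450 |
| 2% | 90% | 5% | 6.7% | +4.7 | 0.49 | 20 | 490 |
| 2% | 100% | 10% | 11.8% | +9.8 | 0.63 | 0 | 980 |

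The first and last rows are the extremes of the grid. The bias does not depend on n, so a larger cohort narrows the interval without moving its centre. The third row shows near-cancellation: the total is almost right, yet 98 of the 198 patients counted were not referred and 100 referred patients are missing. A description of who is referred would still be wrong.

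**4. Restrict F.** Sections 5.2.2.6 and 5.2.2.7 expect few hospital admissions in this cohort, which makes the upper values of F less plausible for inpatient stays. With F at 2% or less, the same grid gives a bias from −10.0 points to +1.96 points (p = 2%, Se = 100%, F = 2%: 2.0 + 1.96 = 3.96%).

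**The case against.** The best defence has four parts.

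- **The wording in Section 5.2.2.4 names a data source, and qualifying episodes can be defined in the statistical analysis plan.** This stands in part. A filter on route, diagnosis or timing, set in a plan not shown here, could remove many unreferred contacts. No filter on HES episodes can recover a referral that produced none.
- **Sections 4 and 5.2.2.4 are compatible.** This stands. Section 5.2.2 defines the CPRD cohort as CPRD Gold linked with HES, so Section 4 describes the linked data. A reader might infer that Section 4 makes HES unnecessary; it does not. Section 2.3 reports referral counts from CPRD (for example 3,045 instances in 913 patients to district nursing), so the records do yield referrals. Those counts are for community services and say nothing about how completely GPs record hospital referrals.
- **The precision statement is tied to sample size.** This stands, as step 2 shows. A reader might infer that the protocol's referral frequency is wrong, or inflated by some factor. No such frequency is stated, and any multiplier would rest on assumptions alone.
- **Workstream 1 asks about referral directly.** This stands as a limit on the consequence: surveys of nurses and surgeons cover referral decisions and barriers, and the CPRD frequency is one descriptive item among several inputs to Workstream 3.

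Two further readings should also be avoided. The rule does not lose every referral that stops short of admission, because outpatient episodes are linked. Nor does it necessarily count one referral several times, because nothing in the protocol says that episodes, and not patients, are the unit.

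**Conclusion.** The point holds as a fault of measurement validity. The HES-derived item can both under-count and over-count referrals to secondary care. The under-count is limited to referrals with no inpatient or outpatient episode. The over-count depends on which episodes are allowed to qualify, which the protocol does not say.

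Size and direction cannot be derived from the documents. The range of −10.0 to +9.8 points rests entirely on the assumed values above, and the errors may nearly cancel in the total. What does not depend on those values is that sample size leaves this error untouched, so the statement in Section 5.2.2.6 should be read as covering sampling error only.

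The sections also disagree on whether referral to secondary care is a CPRD outcome: it is absent from Section 5.2.2.5 and present in Section 5.2.2.6. The matter is confined to the descriptive work under Objective 3; the comparison of surgery with no surgery uses the HES cohort and is not affected.

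**What to change.** - In Section 5.2.2.4, call the HES-derived item hospital contact (linked HES admission or outpatient attendance).
- Report referrals to secondary care separately, from referral entries in the CPRD records already requested, as far as GPs recorded them.
- Cross-tabulate the two by patient: referred and seen; referred and not seen; seen without a recorded referral.
- Align Sections 4, 5.2.2.4, 5.2.2.5 and 5.2.2.6 on whether each item is an outcome and from which source it comes.
- In Section 5.2.2.6, limit the precision statement to sampling error.

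The cost is protocol wording and a code list for secondary-care referrals, since Table 2 covers only referrals and discharges within primary care. No additional data request should be needed, because all CPRD records for these patients are already to be linked. The drawback is that GP recording of hospital referrals may be incomplete. HES contact should therefore stay as a complementary measure and not be replaced; the group seen without a recorded referral will contain both unrecorded referrals and truly unreferred contacts, and should be described as such.
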